Official title: Randomized Trial of a Technology-based Positive Emotion Intervention for Informal Caregivers of Individuals With Alzheimer's Disease

Brief title: Life Enhancing Activities for Family Caregivers (LEAF 2.0)

NCT#: NCT03610698

Date: 10/20/2025

Demographic characteristics, including age, gender, race, ethnicity, income, education, and residence were summarized for the sample as a whole, and by intervention group (Facilitated Intervention, Self-Guided Intervention, and combined Control). Differences between groups were calculated using one-way ANOVA for continuous variables and Chi-squared tests for categorical variables; Fisher's exact tests were used when required by the distribution. Baseline scores for each outcome were compared across the three groups using ANOVA and Kruskal-Wallis tests, depending on the distribution of the data.

Change over time and differences within- and between- intervention groups were assessed using mixed effects linear regression models. Time (baseline, post-intervention, follow-up 1 and follow-up 2) was treated categorically to allow for slope estimates to differ between consecutive timepoints. Models included a random effect for intercept and time. From these models, within-group and between-group differences across intervention groups (Facilitated, Self-Guided, and Control) were estimated between baseline and each follow-up time point (post, FU1, and FU2) using least square means estimates. Effect sizes were calculated to compare change over time across intervention groups.

Lastly, we calculated the number of sessions/weeks completed for each participant during their intervention period to assess how the number of weeks completed moderate the effect of intervention on change in each outcome. We used mixed effects linear regression models including time, intervention group, and usage (none, some, or all sessions) to estimate the change from baseline to each follow-up (post, FU1, and FU2) in both intervention groups, and test for significant change both within and across intervention groups (facilitated, self-guided).

All analyses were performed using SAS v. 9.4; p-values were considered significant at $p < 0.05$.

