PROTOCOL TITLE:

Life Enhancing Activities for Family Caregivers (LEAF) 2.0

PRINCIPAL INVESTIGATOR:

[name], MPH

Professor || Department of Medical Social Sciences || Northwestern University

Director of Research || Osher Center for Integrative Medicine

Director || BSIS Core, Third Coast Center for AIDS Research

[contact]

[contact]

CO-INVESTIGATORS:

[name]

Research Assistant Professor

Department of Medical Social Sciences || Northwestern University

[contact]

[contact]

[name]

Assistant Professor

Department of Medical Social Sciences || Northwestern University

[contact]

[contact]

VERSION DATE:

December 10, 2020

1.0 Purpose of the study:

The Life Enhancing Activities for Family Caregivers (LEAF) 2.0 Course is an intervention containing a series of positive emotion skills for the family caregivers of individuals with Alzheimer's Disease (AD) (1R01AG05613-01). LEAF 2.0 builds upon the LEAF 1.0 intervention (R01NR014435) in that it specifically targets positive emotion, focuses on the caregiver, is a multicomponent intervention that offers an array of skills, and offers online delivery (either facilitated or self-guided) which makes the intervention accessible and convenient.

We will conduct a 3-arm randomized controlled trial with 500 total caregivers of individuals with AD. 200 will be assigned to the web-based facilitated LEAF program (Condition 1), 200 assigned to the web-based self-guided LEAF program (Condition 2), and 100 will be assigned to the emotion reporting waitlist-control condition (Condition 3) with crossover to the either the facilitated version or to the self-guided version; 50 in each condition, respectively. The crossovers take place after approximately 7 months into the study. Participation in the study lasts about 14 months.

LEAF 2.0's three main aims are:

Aim 1: To compare the effect of online self-guided and facilitator-guided delivery modes of LEAF to an emotion-reporting control condition on positive affect, depression, anxiety, and perceived stress.

Aim 2: To explore the effects of LEAF on caregiving burden, self-efficacy, positive aspects of caregiving, quality of care, and AD patient quality of life and assess whether these effects on outcomes are mediated by improvements in positive emotion.

Aim 3: To test whether caregiver age, gender, or baseline stress (dementia severity) moderate the effects of the intervention.

2.0 Background / Literature Review / Rationale for the study:

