- If a participant consents “Yes,” they will automatically continue on to complete the online baseline assessment (T1).
- If an individual does not respond to the consent form, our study team will follow-up with a reminder up to 3 times by phone or email (based on information provided on the screener).
- If an individual responds “No” and declines to participate, they will see a message thanking them for their time, and answer a brief (optional) question about why they declined.

Consenting individuals will continue to take the baseline assessment (T1) which takes up to 1 hour. Once the baseline assessment is complete, participants will be randomized to either the Facilitated LEAF “Video Session” Group (N=200), Self-guided LEAF “Online Lessons” Group (N=200), or an emotion reporting waitlist control. Both the “Online Lessons” and “Video Sessions” consists of 6 modules for the intervention; one-module unlocked per week over 6 weeks, but participants will have an 8-week period to complete the 6-module intervention. The emotion reporting control group reports their daily emotions for 8-weeks (equivalent to the 8-week intervention period), and then crosses over to receive the intervention at time point 4 (T4) as either the “Video Sessions” (N=50) or “Online Lessons” (N=50), after a waiting period of 7 months. Home practice exercises and the daily emotion check-ins will be done over the internet on the Bright Outcome platform for all research arms (N=500). The intervention content, emotion reporting forms, and assessment questionnaires are all mobile-enabled so can be completed on desktop, laptop, tablet, or smartphone.

Randomization:

Condition 1: one-on-one video sessions with a facilitator

Condition 2: self-guided online lessons

Condition 3: emotion reporting condition that will get either the one-on-one video sessions or self-guided online lessons later

Mailing and Receiving a Tablet

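### The SAP's baseline significance tests can flag only chance and feed no step of the analysis, while its main model uses none of the T1 variables named in Aim 3

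*SAP*

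**What the plan says.** The first analysis paragraph of the SAP describes two sets of baseline tests. For demographics: "Demographic characteristics, including age, gender, race, ethnicity, income, education, and residence were summarized for the sample as a whole" and by group, and then "Differences between groups were calculated using one-way ANOVA for continuous variables and Chi-squared tests for categorical variables", with Fisher's exact test where needed. For outcomes: "Baseline scores for each outcome were compared across the three groups using ANOVA and Kruskal-Wallis tests, depending on the distribution of the data". The closing sentence sets a 0.05 significance level for all analyses.

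The protocol (section 8.0, consent, baseline and randomization) fixes the order of events: "Once the baseline assessment is complete, participants will be randomized".

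The SAP's main model is a mixed linear regression with time as a four-level category that includes baseline, and random effects for intercept and time. Groups are compared on change from baseline to each follow-up. No other covariate is named. The last model adds only usage.

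Aim 3 (protocol section 1.0) is: "To test whether caregiver age, gender, or baseline stress (dementia severity) moderate the effects of the intervention". Age and gender appear in the SAP only among the summarized and tested demographics. Dementia severity does not appear in the SAP.

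**The concern.** Because T1 comes before allocation, the null hypothesis of each baseline test is true by design unless randomization failed. A p-value below 0.05 therefore tells the reader nothing about comparability, and one above 0.05 does not show that an imbalance is too small to matter. What matters for the treatment estimate is the size of an imbalance and how strongly the variable predicts change. The tests measure neither.

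The SAP attaches no action to the tests and names no prognostic covariate. An imbalance in age, gender or dementia severity that happens to predict change would stay in the LEAF-versus-control contrast, and the precision available from these T1 variables goes unused. At stake are a baseline table that may cast doubt on sound randomization, and contrasts less precise than the collected data allow.

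**Working it through.** **Inputs.** From the protocol: allocation 200/200/100 (section 4.0), and detectable effects of d=.34 for 100 versus 200 and d=.31 for 100 versus 400 (section 8.0, Power). From the SAP: 7 listed demographics and the 0.05 level. The SAP does not list its outcomes. The protocol names 4 in Aim 1 ("on positive affect, depression, anxiety, and perceived stress") and 5 in Aim 2 ("To explore the effects of LEAF on caregiving burden, self-efficacy, positive aspects of caregiving, quality of care, and AD patient quality of life"), which gives 9. Outcomes are taken in SD units.

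**Protocol figure reproduced.** For 100 versus 400, the detectable d at 80% power is (1.96 + 0.84) × √(1/100 + 1/400) = 0.313. At d=.31 the power is 79.2%. The stated figure holds.

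**False alarms at baseline.** There are 7 + 9 = 16 tests.
- Expected number: 16 × 0.05 = 0.8.
- Chance of at least one if independent: 1 − 0.95^16 = 0.56.
- Simulated with the 9 outcomes correlated 0.5 and 0.7 (assumed): 0.50 and 0.45.
- With only the 4 Aim 1 outcomes (11 tests): 1 − 0.95^11 = 0.43 if independent, 0.40–0.41 if correlated.

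**Largest imbalance the ANOVA leaves unflagged.** If control differs by d from both LEAF arms, the between-group sum of squares is 400 × (0.2d)² + 100 × (0.8d)² = 80d². The critical value of F(2,497) is 3.014, so d = √(2 × 3.014/80) = 0.274 SD. This is one configuration, not a ceiling: a single LEAF-control pair can differ by up to √(2 × 3.014 × (1/100 + 1/200)) = 0.301 SD.

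**How often that happens.** The SE of a chance difference, 100 versus 400, is √(1/100 + 1/400) = 0.112 SD.
- 0.274/0.112 = 2.45 SE, a two-sided probability of about 1.4% per variable.
- The median absolute imbalance is 0.6745 × 0.112 = 0.075 SD.

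**Carry-over to the contrast.** The shift is the imbalance times the variable's correlation with change. The documents give no such correlation; 0.2–0.3 is assumed. The denominator is the protocol's d=.31 for 100 versus 400.

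| Imbalance | Shift at 0.2 | Shift at 0.3 | Share of .31 |
|---|---|---|---|
| 0.075 SD (median) | 0.015 | 0.023 | 5–7% |
| 0.274 SD (rare) | 0.055 | 0.082 | 18–27% |

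**The outcome's own baseline.** The change contrast subtracts the baseline imbalance in full, but only a fraction rho (the baseline to follow-up correlation) is expected to persist. Given an imbalance, the contrast is therefore off by −(1 − rho) × imbalance. For 0.27 SD this is −0.19, −0.11 and −0.05 SD at rho = 0.3, 0.6 and 0.8 (assumed). A simulated random-intercept mixed model at rho = 0.6 with no treatment effect gave −0.109. Outcome variance at rho = 0.6 is 2(1 − 0.6) = 0.80 for change against 1 − 0.6² = 0.64 for ANCOVA, a 20% reduction.

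**The case against.** The strongest reply is that nothing here invalidates the analysis. Randomization makes the unadjusted contrast unbiased on average, and its standard error already allows for chance imbalance. A false positive in the baseline table changes no treatment estimate, since the SAP conditions on none of these tests. Summaries by arm are already planned for demographics. All of this stands, and it limits the point to precision, bias conditional on the imbalance that occurs, and reporting.

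A reader might go further in four ways that the documents do not support.
- That baseline imbalance in the outcomes is left uncorrected. It is not: baseline is a level of time and groups are compared on change. The remaining problem is over-correction.
- That p > 0.05 will be taken as proof of balance. The SAP contains no such rule and does not select covariates by p-value.
- That a spurious significant difference is likely. That depends on the test count. Counting all 22 scales in the T1 column with the 7 demographics gives 1 − 0.95^29 = 77% if independent, but the SAP does not say that every T1 scale is an outcome.
- That 0.27 SD is a typical hidden imbalance. It is a 1.4% event per variable.

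The SAP is dated October 2025 and written in the past tense, so adjustment added now cannot be presented as pre-specified. Aim 3 also names its variables as moderators; that they predict change is an assumption.

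**Conclusion.** The point holds as a matter of efficiency and reporting, not validity. The baseline tests are uninformative and lead nowhere: about 0.8 false positives are expected in 16 inferred tests, with a 45–56% chance of at least one. The main model leaves out three T1 variables that the protocol itself singles out. The usual cost of a chance imbalance in one such variable is small (a shift of about 0.015–0.023 SD), and the rare cost is 0.05–0.08 SD. If the covariates explain 5–10% of the variance in change (assumed), adjustment cuts the contrast variance by the same share. Better handling of the outcome's own baseline offers more: 20% at rho = 0.6 for a single follow-up.

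These sizes rest on the planned 200/200/100, on the inferred test count, and on correlations the documents do not give. The SAP reports no analysed sample size, and protocol section 10.0 records recruitment difficulty. With fewer participants, chance imbalances and the unflagged limits would be larger.

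**What to change.** 1. Add caregiver age, gender and T1 dementia severity to the mixed model as fixed covariates, each with a time interaction, whatever imbalance is observed. Taking them from Aim 3 keeps the choice independent of the data.
2. Name the severity scale. The Measures text in protocol section 8.0 makes the Revised Memory and Behavior Problems Checklist the proxy for severity, while the Table of Measures also lists the Dementia Severity Rating Scale.
3. Keep baseline as a response but constrain its mean to be equal across arms, which randomization after T1 justifies, or use ANCOVA. The covariates in item 1 do not deal with the over-correction; this step does.
4. Report the SAP's existing model beside the adjusted one. If data have already been analysed, label the adjusted model as added after the SAP.
5. Replace the baseline ANOVA, Kruskal-Wallis, chi-squared and Fisher p-values with summaries by arm and standardized differences of each LEAF arm from control. This is a reporting change only and alters no treatment estimate.

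The cost is revised SAP wording, a rerun of existing SAS code and a few degrees of freedom. No new data are needed.

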The goal of the proposed intervention, called LEAF (Life Enhancing Activities for Family Caregivers) is to reduce burden and increase well-being in Alzheimer’s Disease caregivers through the practice of positive emotion skills. We will evaluate two methods of online delivery of LEAF: facilitated and self-guided and compare them to an emotion-reporting waitlist control condition. If effective, the LEAF program can be disseminated to Alzheimer’s caregivers nation-wide.

3.0 Inclusion and Exclusion Criteria:

Inclusion criteria:

- Age 18 and over
- Identifies as the primary family caregiver of a person with Alzheimer’s Disease (AD)
- Speaks and reads English
- Has access to high speed internet connection at home or in a location where they can speak privately with a facilitator (e.g. a library)

4.0 Sample Size:

We will recruit a total of 500 participants nationwide into the LEAF 2.0 randomized controlled trial. Once participants complete the online consent and baseline questionnaire, they will be randomized 2:2:1 to Facilitated LEAF (N = 200), Self-guided LEAF (N = 200) or emotion reporting waitlist control (N = 100). The waitlist control group will crossover during the study to receive either the Facilitated LEAF (N = 50) or the Self-guided LEAF (N = 50).

5.0 Research Locations:

Research will be based at Northwestern University's (NU) Feinberg School of Medicine through the Department of Medical Social Sciences (MSS) as the lead research site. NU holds the IRB of record. The research will involve Bright Outcome (<https://www.brightoutcome.com/>), a company experienced in designing online platforms for patient reported outcomes research. Bright Outcome has a proven track record of collaboration and delivery of technology products/services to investigators at the Feinberg School of Medicine.

6.0 Multiple sites:

Northwestern University is the lead (primary) research site for the LEAF 2.0 Study. The University of California San Francisco (UCSF) is the secondary research site for the LEAF 2.0 Study. The Principal Investigator ([name]), co-Investigators ([name] and [name]), the NU Project Director ([name]) are at NU, in addition to the several team members who are doctoral students mentored by [name], and other research assistants on the project. Only IRB-approved staff will have contact with participants.

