Simple group comparisons for single time points or pre-post comparisons between the facilitated (n=200) and self-guided (n=200) groups will have 80% power to detect effect

sizes of $d=.28$ ($R^2=.019$), below the observed effect sizes for positive emotion, negative emotion, stress, depression, and anxiety in our previous LEAF trial. Comparisons between the wait-list control group ($n=100$) and the LEAF interventions individually ($n=200$) or taken together ($n=400$) will have 80% power to detect effect sizes of $d=.34$ ($R^2=.029$) and $d=.31$ ($R^2=.024$), respectively.

Our design of seven time points and 500 individuals exceed established minimums for detecting predictors of individual differences¹⁰⁸ and for detecting associations between parallel growth processes.¹⁰⁹ Power for these models was estimated by Monte Carlo simulation to account for our longitudinal experimental design. Effects of observed predictors (i.e., LEAF group, Aim 1) had 80% power for effects of $d=.27$ ($R^2=.018$). Parallel growth curves showed 80% power for slope correlations of $r=.14$ ($R^2=.019$), and comparable power for indirect effects of ($r=.15$, $R^2=.021$), consistent with previous work on mediational power.¹¹⁰

Missing Data

Although our previous test of LEAF showed high adherence rates and minimal dropout, all longitudinal analyses must plan for missing data. All proposed models will be fit with full information maximum likelihood, which yields unbiased parameter estimation under common missing data mechanisms. Multiple imputation will be used in any cases where covariates predict missingness but would otherwise not be included in proposed models.

9.0 Incomplete Disclosure or Deception:

N/A

10.0 Recruitment Methods:

We plan to recruit participants over the period of 42 months. Recruitment efforts will target the 2 major national organizations servicing patients with dementia and their caregivers: 1) the Alzheimer's Association and 2) the Family Caregiver Alliance: National Center on Caregiving.

We will also use print, radio, and websites at the national and local level of these organizations to access a geographically and age diverse cohort. Subjects will also be recruited from the Northwestern University Alzheimer's Center, the University of California San Francisco Memory and Aging Center, The New Normal, and the NUCATS recruitment tool. We will also recruit on Alzheimer's-related websites that give us permission to post.

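### The SAP gives categorical time a random effect without defining it or naming a covariance structure; depending on the model fitted, the FU2 or post contrast may miss its 5% level

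*SAP*

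**What the plan says.** The SAP's paragraph on change over time describes mixed-effects linear regression. On the mean structure it says: "Time (baseline, post-intervention, follow-up 1 and follow-up 2) was treated categorically to allow for slope estimates to differ between consecutive timepoints". The next sentence is all it says about within-person dependence: "Models included a random effect for intercept and time". Within- and between-group changes "were estimated between baseline and each follow-up time point (post, FU1, and FU2) using least square means estimates", and the closing paragraph sets the threshold at 0.05 without stating sidedness.

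The SAP names no type of random-effects matrix, residual structure, degrees-of-freedom method, robust standard error or convergence fallback. The protocol (section 8.0, Missing Data) adds only that models use full information maximum likelihood. Neither document gives a within-person correlation or a dropout rate.

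**The concern.** That one sentence sets the standard error of every efficacy contrast. Each contrast is a change from baseline, and its variance depends on the correlation between baseline and that particular visit. A covariance model that forces those correlations into the wrong pattern gives wrong standard errors, too small at some visits and possibly too large at others, even when the estimated differences are sound.

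A random effect of categorical time within person, with one record per visit, is also an unusual thing to fit. A reader cannot tell from the SAP which of several quite different models lies behind the p-values. If there is dropout, the likelihood's protection under missing-at-random also relies on a correct covariance, so the estimates could be affected too. With no dropout rate in the documents, that part is not sized here.

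**Working it through.** **The plan's own figures.** The only operating figures are in the protocol's Power section: 80% power at d = 0.28 (200 vs 200), 0.34 (100 vs 200) and 0.31 (100 vs 400). With power = Φ(d·√(n₁n₂/(n₁+n₂)) − 1.96):
- 0.28 × √100 = 2.80, power 79.96%
- 0.34 × √66.67 = 2.78, power 79.3%
- 0.31 × √80 = 2.77, power 79.2%

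These reproduce. They concern simple group comparisons and do not bear on the mixed model's covariance.

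**Inputs.** Four assessments, categorical fixed time, and changes from baseline tested at 0.05 (SAP; two-sided assumed). Survey invitations on days 0, 84, 140 and 196 for T1-T4 (Protocol, Schedule of Measurements by Timepoint); taking these as baseline, post, FU1 and FU2 is my reading. Correlations are assumed. Data are taken as complete and normal, with equal variances over time.

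**Step 1: what each reading can estimate.** A 4×4 covariance matrix has 4×5/2 = 10 distinct elements.
- *Categorical random time, variance components.* The diagonal is σ²(intercept) + σ²(time) + σ²(residual) and every off-diagonal is σ²(intercept). Only the sum of the last two variances is estimable: 3 parameters, rank 2. This is compound symmetry.
- *Random intercept plus three time contrasts, unstructured.* 10 parameters plus the residual make 11, for 10 elements (rank 10). The split is not identified, but the marginal covariance is.
- *Random intercept and linear slope, with categorical fixed time.* 4 parameters, rank 4. It is estimable and does not force a constant correlation.

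**Step 2: actual level of each contrast.** With complete data and a separate mean for each arm and visit, the estimates do not depend on the covariance model; only the standard errors do. The true variance of a change is proportional to 2(1 − ρ), with ρ the correlation of baseline with that visit. The arm-size factor cancels from the ratio. The best-fitting compound symmetry uses the average r̄ of the six correlations, so its variance is proportional to 2(1 − r̄). Then

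level = 2[1 − Φ(1.96·√(model variance / true variance))].

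Example, correlations .70/.65/.60 at one, two and three visits apart: r̄ = (3×.70 + 2×.65 + .60)/6 = .667 and the model variance is 0.667. The true variances are 0.60, 0.70 and 0.80. The SE ratios are 1.054, 0.976 and 0.913, giving levels of 3.9%, 5.6% and 7.4%.

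The linear-slope column uses the closest-fitting (Kullback-Leibler) covariance of that form, with time in days.

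| Assumed correlations | Compound symmetry: post / FU1 / FU2 | Linear slope: post / FU1 / FU2 |
|---|---|---|
| Constant .60 | 5.0 / 5.0 / 5.0% | 5.0 / 5.0 / 5.0% |
| .70/.675/.65 by lag | 4.4 / 5.3 / 6.2% | 4.8 / 5.0 / 4.9% |
| .70/.65/.60 by lag | 3.9 / 5.6 / 7.4% | 4.5 / 5.0 / 4.8% |
| .7/.6/.5 by lag | 3.0 / 6.1 / 9.3% | 4.1 / 5.0 / 4.7% |
| AR(1) .7 | 1.9 / 7.2 / 11.3% | 3.3 / 5.4 / 4.3% |
| AR(1) .8 | 1.6 / 7.3 / 12.4% | 3.2 / 5.3 / 4.4% |
| Baseline with follow-ups .60, between follow-ups .70 | 6.7% at all three | 7.2 / 6.3 / 5.1% |
| .50 and .70 | 8.0% at all three | 9.1 / 7.2 / 5.1% |
| .55 and .75 | 8.4% at all three | 9.7 / 7.5 / 5.1% |

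The last three rows describe people who respond by different amounts between baseline and post and are stable afterwards. With equally spaced time in place of days, the linear slope's FU2 level in those rows is up to about 6%.

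**Step 3: simulation.** 20,000 trials at 200/200/100, testing one 200-person arm against control, for constant .60, .70/.65/.60, .7/.6/.5 and AR(1) .7. Compound symmetry gave FU2 levels of 5.0%, 7.4%, 8.9% and 11.1%. Unstructured covariance gave 4.5-5.0% at all three visits in every case.

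**The case against.** A reader might infer that the model either cannot be estimated or must be compound symmetry, that its standard errors are therefore wrong, and that FU2 false positives run at 7-10%. The documents do not support that, for four reasons.

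- Time is categorical in the SAP for a stated purpose, to let change differ between successive visits, and that concerns the mean. Categorical fixed time with a random intercept and linear random slope is an ordinary, estimable model. It keeps FU2 at 4.3-5.1% in the table.
- Unidentified components are not the same as wrong standard errors. The unstructured block can reproduce any positive-definite 4×4 covariance, so if it converges it gives the same contrast standard errors as the unstructured model proposed here.
- Even under compound symmetry, the level is exactly 5% with constant correlation and 6.2% with slight decay. The 7-10% band needs moderate decay, and the documents give no correlations.
- Nothing in either document shows that compound symmetry was fitted.

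All four stand, and they limit the point to a conditional one. They do not remove it. The sentence leaves the model undefined, and neither restricted reading holds 5% at every visit across plausible correlation patterns. The linear slope protects FU2 but can inflate post, the contrast straight after the intervention period.

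**Conclusion.** The covariance model behind every efficacy contrast is undefined, and its literal reading is either compound symmetry or over-parameterised. Harm is possible but not established:

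- Compound symmetry: FU2 level 5% with constant correlation and about 6-12% with decay over visits, with post then at about 2-4%. If baseline correlates less with the follow-ups than they do with each other, all three contrasts run at about 7-8%.
- Linear slope: FU2 near 5%, with post at about 7-10% under that same baseline pattern.
- Unstructured random block: contrast standard errors can be correct if the fit converges.

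These sizes assume complete data, equal variances over time, normal outcomes and the correlations shown. This is a should-fix: a cheap improvement, with inflation conditional on correlations that the documents do not give.

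**What to change.** Replace the random-effects sentence with: *Within-person covariance over the four assessments is unstructured (REPEATED time / SUBJECT=id TYPE=UN), with Kenward-Roger degrees of freedom; if the model does not converge, a heterogeneous Toeplitz structure with empirical (sandwich) standard errors is used.* The particular fallback is a matter of choice; what matters is that one is stated.

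Drop the random intercept and random time terms and re-run the contrasts. Because the SAP describes the analyses in the past tense, also report which structure was originally fitted. The session-usage models, for which no covariance is given either, should state theirs. A repeat with arm-specific covariance (GROUP=arm) is optional.

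The cost is one sentence and a re-run. Ten covariance parameters in place of two to four are negligible for a planned 500 people.
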